4.3. Intensive Sampling Phase

Approximately 40 viremic subjects (up to a maximum of 60) will be asked to participate in more intensive sampling. Those subjects in whom BK viremia is identified (by PCR result demonstrating BK DNA $\geq 10,000$ copies/ml) will be shifted to a more intensive sampling schedule. A review of the informed consent will be initiated by the research staff to confirm the subject's continued willingness and ability to participate in the intensive monitoring phase until resolution of viremia or until another discontinuation event occurs.

Blood and urine specimen collection will occur every 2 weeks, \pm 7 days, until the BK viremia has resolved (or another study termination endpoint is reached). Resolution of BK viremia is defined as PCR becoming negative (or viral load <1000 copies/ml). Start and stop dates for the Intensive Sampling Phase will be defined by the date that the qualifying (initial positive and subsequent negative) blood samples were drawn.

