5. STUDY POPULATION

5.1. Study Population Selection

All adult renal or renal-pancreas transplant patients who meet protocol inclusion/exclusion criteria are eligible for participation in this study.

In an effort to capture subjects early in the course of the evolving BK infection and avoid subjects who have already developed evidence of BKVN, this protocol will emphasize consent in the early peri-transplant period. Patients may be consented while hospitalized pre-transplantation (as early as 7 days prior to transplantation) or at an outpatient follow-up visit (as late as 100 days post-transplantation). The study enrollment visit and initial collection of protocol-defined specimens will take place between 4 weeks and 100 days following renal or renal/pancreas transplantation.

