8.2. Sample Size Considerations

8.2.1. Sample Size

[figure not shown]
We propose to enroll approximately 450 (up to a maximum of 518) patients in this study. The sample size justification is based on observing a target number of BKV viremia patients from the patients enrolled in the screening group. Table 1 below shows varying values of proportion of patients with BKV viremia. Figure 1 summarizes the probability of observing K number of BKV patients (K=30, 35, 40, 45, and 50) assuming varying values of true proportion of BKV viremia patients (3% to 17%) out of 450 enrolled patients. To interpret this graph, assume that the true proportion of BKV viremia patients is 10%. Then the probabilities of observing at least 30, 35, 40, 45, and 50 BKV viremia patients out of the 450 enrolled are about 0.99, 0.94, 0.76, 0.46, and 0.19, respectively.

In this study, we would like to target approximately 40 BKV viremia patients (up to a maximum of 60). From Figure 1, enrolling 450 subjects give us at least 90% probability of identifying at least 40 BKV viremia patients, if the true percent of BKV viremia patients is at least 11%.

Table 1

Location	Study Type	Sample size (N)	% with BKV viremia	Reference
USA ³	Prospective	200	11.5%	Brennan 2005
Spain ⁵	Prospective	156	12.2%	Munoz 2005
USA ²³	Prospective	66	16.6%	Petrov 2009
Czech Republic ²⁴	Prospective	120	6%	Girmanova 2011
USA ²⁵	Retrospective	134	16%	Koleilat 2011

Figure 1: Probability of Observing a Given Number of BKV Subjects or More as a function of True Percent with BKV viremia

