We are also interested in comparing the change in GFR between those with and without BKV viremia. In this power analysis, we will only be concerned about the change from baseline (time of enrollment) to Month 12 (time post-transplant). Assuming the standard deviation of the change in GFR is assumed to be the same for those with and without BKV viremia and equals 10.9 ml/min/1.73 m² (Ref: Srinivas TR, Flechner SM, Poggio ED, et al. Glomerular filtration rate slopes have significantly improved among renal transplants in the United States. Transplantation 2010; 90:1499-505.). With 40 BKV viremia subjects and 410 non-BKV viremia subjects, we will detect a mean difference in the change in GFR of at least 5.9 ml/min/1.73 m² with 90% power between these two groups of subjects at 5% level of significance based on a t-test. In the final analysis, we will be using all available GFR data for each subject which should increase the power as more information is used. This will enable us to still use data from subjects who dropped out before the end of the study.

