8.4.1. Primary Outcome Analysis

Incidence of BK viremia will be estimated using a 95% confidence interval for single proportion. Logistic regression will be used to investigate the risk factors for BKV viremia and BKVN. Factors will include:

- Donor-derived factors:
 1. Deceased donor – Standard criteria donor (SCD), Donor after cardiac death (DCD), Expanded criteria donor (ECD)
 2. Living donor – related donor or unrelated donor
 3. ABO incompatibility
 4. Total HLA mismatches
 5. HLA C7 status
 6. Race/ethnicity
 7. Sex
- Recipient-derived factors:
 1. Delayed graft function (DGF), defined as use of dialysis within 7 days of the transplant
 2. Cold ischemia time (CIT)
 3. Warm ischemia time (WIT)
 4. Use of stents
 5. HLA C7 status
 6. Type/intensity of immunosuppression, including corticosteroids
 7. Acute rejection
 8. Age
 9. Race/ethnicity
 10. Sex

To compare the change in GFR over time between those with and without BKV viremia, we use all available GFR data from each subject. We will use mixed model for repeated measures to analyze the GFR data over time. This analysis method will allow us to use any of the available GFR data

even if they are not complete. We will determine the appropriate covariance structure to use as indicated by the Akaike Information Criterion.

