8.4.2. Secondary Endpoints

The distribution of the time to onset and duration of BKV viremia will be estimated using survival analysis methods such as Kaplan-Meier estimator for a single group. This will provide estimates of the median time to onset or median duration of BKV viremia. To compare different groups and/or determine risk factors, we will use Cox proportional hazard regression model if the proportional hazards assumption is found to be reasonable. Otherwise, we will consider using parametric survival regression models (in particular, accelerated failure time model). Parametric regression models are useful especially in cases where sample sizes are small or when the percent censored is high. This will also be the tool of preference if there will be left-censored subjects, i.e., subjects who at enrollment show evidence of BK viremia. Cox model cannot handle left-censored data.

As with the BKV viremia, incidence of BKVN will be estimated using a 95% confidence interval for single proportion. We will utilize logistic regression to compare groups, or adjust for covariates or determine risk factor.

To investigate the change in the quantitative BK viremia over time and how it is associated with important factors such as the use of immunosuppressive therapy and recipient's demographic and clinical characteristics, we will again use mixed regression modeling for repeated measures.

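### Section 8.4.2 promises a Kaplan-Meier median time to onset of BK viremia that will almost certainly not be reached; the simple incidence proportion in 8.4.1 can also be improved cheaply

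*Combined protocol and SAP*

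**What the plan says.** Time to onset is part of the first primary objective (3.1.1) and is the first secondary endpoint (3.2.2), counted in days from transplantation. Section 8.4.2 estimates the distributions of time to onset and of duration by survival methods, with a single-group Kaplan-Meier estimator as the example, and continues: "This will provide estimates of the median time to onset or median duration of BKV viremia". No other summary is named in case the median is not reached. Heavy censoring is foreseen, but only as a reason for choosing a regression model: "Parametric regression models are useful especially in cases where sample sizes are small or when the percent censored is high". On subjects already viremic at entry, the section says of parametric regression: "This will also be the tool of preference if there will be left-censored subjects, i.e., subjects who at enrollment show evidence of BK viremia".

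For the primary endpoint, 8.4.1 says: "Incidence of BK viremia will be estimated using a 95% confidence interval for single proportion". Section 3.2.1 places that incidence in the screened population. Section 8.4 rules out imputation. Neither 8.4 nor 8.4.1 states the denominator or how subjects who leave early are counted.

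The expected frequency is about 10-15% (2.1.1 and 2.2.1). Section 8.2.1 draws Figure 1 "assuming varying values of true proportion of BKV viremia patients (3% to 17%) out of 450 enrolled patients". Its GFR power calculation begins "With 40 BKV viremia subjects and 410 non-BKV viremia subjects". On entry, 5.1 says: "The study enrollment visit and initial collection of protocol-defined specimens will take place between 4 weeks and 100 days following renal or renal/pancreas transplantation". Under 4.2, screening of subjects without qualifying viremia ends about 12 months after transplantation, or earlier for death, graft failure, re-transplantation, chronic dialysis, withdrawal, investigator decision or study closure.

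**The concern.** A Kaplan-Meier median exists only if the curve falls to 0.5. When subjects who never become viremic are censored, as the section's own remarks on censoring suggest, that requires onset in about half the cohort. Nothing in the protocol points to a frequency near that. The one numerical summary named for time to onset would be unavailable, and its replacement would be chosen after the data are seen.

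The second matter is smaller. A simple proportion over everyone screened treats a subject who withdraws at Month 4 like one followed without viremia to Month 12. If some leavers would later have become viremic, 12-month incidence is understated.

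**Working it through.** **Inputs from the documents.** N = 450 (maximum 518); expected viremia 10-15%; Table 1 studies 6-16.6%; Figure 1 grid 3-17%; target about 40 viremic subjects; entry 4 weeks to 100 days after transplantation; end of screening about Month 12.

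**The plan's own figures.** At a true 10%, 8.2.1 gives probabilities 0.99, 0.94, 0.76, 0.46 and 0.19 for at least 30, 35, 40, 45 and 50 viremic subjects of 450. The exact binomial gives 0.991, 0.936, 0.757, 0.460 and 0.192 for *more than* K, and 0.995, 0.955, 0.805, 0.523 and 0.237 for *at least* K. The printed values are therefore one count off. This is minor and has no bearing here. The statement of at least 90% probability at a true 11% holds either way (0.938 for at least 40, 0.915 for more than 40).

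**Is the median reached?**
- Subjects needed: 450/2 = 225.
- End of the curve without loss is 1 - p: 0.90 at 10%, 0.85 at 15%, 0.83 at 17%, 0.97 at 3%.
- P(at least 225 of 450), exact binomial: 6e-58 at 17%, and still only 6e-19 at 30%.
- Adding 60 patients enrolled directly with known viremia to 17% of 450 gives (60 + 76.5)/510 = 27%, still far from half.
- With loss (assumed; no rate is given), two simulations used the visit schedule. In one, with a fixed last visit, the lowest Month-12 value in 2,000 trials at 17% viremia and 30% leaving was 0.755. In the other, with variable visit windows, the curve reached 0.5 in at most 0.1% of 5,000 runs, only when a last event met a very small late risk set, and never once steps with fewer than 20 at risk were ignored.

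**Duration.** With 40 viremic subjects, the probability that at least 20 resolve under observation is 0.93 if 60% resolve and 0.998 if 70% do (0.56 at 50%). That median may well be estimable.

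**Early leavers and the simple proportion.** With constant hazards over the year, onset a = -ln(1 - p) and leaving b = -ln(1 - d), the expected proportion over all screened subjects is [a/(a + b)] x [1 - (1 - p)(1 - d)]. For p = 0.10 and d = 0.20: a = 0.105, b = 0.223, giving 0.321 x 0.280 = 0.090, so a true 10% reads 9.0%.

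Simulation at a true 12% (n = 450, 2,000 trials per setting) assumed entry uniform over days 28-100, 50-90% of onsets by Month 6, death or graft loss 0-5%, and leaving unrelated to viremia:

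| Leaving (assumed) | Simple proportion, all screened |
|---|---|
| 10% | 11.4-11.7% |
| 20% | 10.8-11.4% |
| 30% | 10.2-11.1% |

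The shortfall is 0.3-1.8 points. The competing-risk cumulative incidence reads 12.0-12.3% over the same settings; the slight excess comes from dating onset to visits. For scale, the 95% half-width with complete follow-up is 1.96 x sqrt(0.12 x 0.88/450) = 3.0 points.

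**The case against.** The section first promises the distribution of time to onset, and the median follows from it. The curve will exist, and Month 6 and Month 12 values can be read from it. That stands: the defect is in the named summary, and a reader who inferred that the onset analysis as a whole fails would go beyond the documents.

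The single group might mean viremic subjects only, as it must for duration. A median onset day then exists, but it is conditional on becoming viremic, and the text does not say that it is. On that reading the label is missing.

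A reader might take 3-17% as the plan's assumption and 60 as a ceiling on onsets. Neither is supported. The first is the plotting grid of Figure 1. The second limits intensive sampling: "Approximately 40 viremic subjects (up to a maximum of 60) will be asked to participate in more intensive sampling". The conclusion rests on the expected 10-15% and needs neither.

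A reader might also infer that the primary incidence estimate is invalid. The documents do not support this. The denominator is an inference from 3.2.1 and the 40/410 split in 8.2.1, the dropout rates are assumed, and the shortfall is below the half-width. If leavers had no later risk, the simple proportion would be right and, with 20% leaving, the competing-risk estimate 0.8 points high.

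Nor does the plan overlook subjects viremic at entry. It names them and prefers parametric regression for them; a parametric fit without covariates could also serve a single group. What is unstated is how they enter the Kaplan-Meier curve.

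**Conclusion.** The sentence on median time to onset is wrong as written on the whole-cohort reading, and unlabelled on the conditional one. At every frequency the protocol mentions, the whole-cohort median will almost certainly not be reached; the wording stops short of certainty because a sparse late risk set can, very rarely, pull the curve down. This conclusion needs no dropout assumption. The curve and the median duration are not affected.

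The early-leaver point is a cheap improvement to the primary estimate, not an error in it. Its size, 0.3-1.8 points at a true 12%, depends on all screened subjects forming the denominator and on an assumed 10-30% leaving.

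**What to change.** **8.4.2 (correction).** Replace the median time to onset with cumulative incidence and 95% confidence intervals at Months 6 and 12. Report any median onset day only as applying to subjects who became viremic. Keep the median for duration, and leave the regression provisions unchanged.

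**8.4.1 (improvement).** Beside the simple proportion, report 12-month cumulative incidence in prospectively screened subjects, with death and graft loss as competing events and other exits censored at the last sample without qualifying viremia.

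**Both sections.** Use one estimator, one time origin (transplantation) and one event definition, the protocol's qualifying viremia (at least 10,000 copies/ml, 4.2 and 4.3), at both landmarks. Count subjects found viremic at the enrollment visit as events by Month 6; entry closes at day 100, so this is always correct. Report patients enrolled directly for known viremia separately, with a sensitivity analysis that includes them.

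**Cost.** SAP wording and standard software; exit reasons are already documented under 4.2.
- The Month-12 half-width is about 3.0-3.4 points with 10-30% leaving, against 3.0 with complete follow-up.
- Other exits must be unrelated to viremia risk. With 20% leaving, if leavers' later risk were half or double, the estimate would be about 0.4 points high or 0.8 low (simple proportion: 0.4 or 1.6 low).
- Dating onset to the first positive sample makes Month 6 read about 5.5, 8.3 and 10.0% against a true 6.0, 9.0 and 10.8% (50, 75 and 90% of onsets by Month 6, assumed). An interval-censored (Turnbull) estimate is an optional check. A Month 3 landmark is also optional, since it falls inside the enrollment window.
- Leaving out direct enrollees could make a true 12% read low. In the extreme case where routine care finds every onset before the enrollment visit, x = 0.0140, 0.0210 or 0.0252 of patients are removed (same three onset patterns), and (0.12 - x)/(1 - x) gives 10.75, 10.11 or 9.72%. Hence the sensitivity analysis.

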BK polyomavirus infection is mediated by direct infection of allograft renal tubular epithelial cells (TECs). Molecular analysis has demonstrated that there is substantial inflammatory injury associated with a profibrotic milieu.¹⁶ Monitoring for infection is performed by detecting viral copies in urine and blood. However, virus is frequently shed in the urine in the absence of invasion leaving the urinary monitoring as a suboptimal screening mechanism in terms of management of recipients that are infected. A testable hypothesis is that tubular injury, in the context of viral infection, indicates invasive disease. Detection of this tubular injury may provide an opportunity to manage kidney graft recipients at an earlier stage before invasive BK disease. Coupled with urine PCR, detection of renal tubular injury in recipient urine is a simple technique. Urine markers of injury have already been identified in other causes of acute kidney injury and are commercially available. These include cystatin C, renin, clusterin, Kim-1, b2-microglobulin, osteopontin, retinol binding protein, and markers of cell apoptosis.

Currently, no antiviral drug is approved for treatment of BKV infection.¹⁷ Anecdotal reports have claimed benefit from cidofovir, leflunomide, quinolone antibiotics, and intravenous immunoglobulin. However, the current standard of care is early screening for BKV viremia and reduction in immunosuppressive therapy in an effort to improve graft survival, although it has not been studied in a controlled fashion.^{12,18,19} At some institutions, modulation of immunosuppressive therapy has dramatically reduced the rate of allograft loss due to BKVN.¹⁴ Reduction in the immunosuppressive regimen is not without consequence and can result in graft loss from immune-mediated organ rejection.²⁰ Despite reduction in immunosuppression, in some studies 30 to 70% of patients with BKVN have progressive deterioration in renal function, eventually resulting in allograft loss. Declining renal function typically occurs over months and is thought to result from a combination of persistent viral infection, organ rejection (induced by reduction in immunosuppression), and renal fibrosis.

This study is being performed to identify the natural history of BK viremia in renal transplant patients with the intent to identify high-risk groups that may benefit in the future from therapy with

safer and more effective antiviral medications.

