3.2.2. Secondary endpoints

- Timing of onset of BK viremia (number of days post-transplant)

- Duration of BK viremia
- Incidence of BKVN in the study population
- Dynamics of quantitative measurements of BK viremia over time
- Frequency of donor and recipient-related risk factors for BV viremia, including:
 - a. Donor-derived factors:
 - i. Deceased donor – Standard criteria donor (SCD), Donor after cardiac death (DCD), Expanded criteria donor (ECD)
 - ii. Living donor – related donor or unrelated donor
 - iii. ABO incompatibility
 - iv. Total HLA mismatches
 - v. HLA C7 status
 - vi. Race/ethnicity
 - vii. Sex
 - b. Recipient-derived factors:
 - i. Delayed graft function (DGF), defined as use of dialysis within 7 days of the transplant
 - ii. Cold ischemia time (CIT)
 - iii. Warm ischemia time (WIT)
 - iv. Use of stents
 - v. HLA C7 status
 - vi. Type/intensity of immunosuppression, including corticosteroids
 - vii. Acute rejection
 - viii. Age
 - ix. Race/ethnicity
 - x. Sex
- Frequency of clinical outcomes that are potentially related to BKV infection, including:
 - a. subject death,
 - b. loss of graft function as defined by GFR <10 mL/min/1.73 m²
 - c. development of urinary outlet obstruction
 - d. development of gross hematuria
 - e. development of lymphocele
 - f. acute rejection
 - g. initiation of dialysis
 - h. re-transplantation
 - i. renal biopsies

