6.4. Subject Early Termination

Subjects will be terminated from the study for any of the following reasons:

- Death;
- Initiation of chronic dialysis for loss of graft function;
- Re-transplantation;
- Inability or unwillingness to comply with study requirements.

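### Kaplan-Meier for duration of viremia censors death and graft loss before clearance, so the clearance curve overstates the proportion of viremic subjects who actually clear

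*Combined protocol and SAP*

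**What the plan says.** "Duration of BK viremia" is a secondary endpoint (3.2.2), and duration is also named in the first primary objective (3.1.1). Section 8.4.2 plans that the "duration of BKV viremia will be estimated using survival analysis methods such as Kaplan-Meier estimator for a single group", and continues: "This will provide estimates of the median time to onset or median duration of BKV viremia". To compare groups it plans a Cox model, or a parametric survival model if proportional hazards fails.

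Section 4.3 sets the event: "Resolution of BK viremia is defined as PCR becoming negative (or viral load <1000 copies/ml". It also says when two-weekly sampling stops: "until the BK viremia has resolved (or another study termination endpoint is reached". Section 6.4 opens its list with "Subjects will be terminated from the study for any of the following reasons" and names death, "Initiation of chronic dialysis for loss of graft function", re-transplantation, and inability or unwillingness to comply.

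Nothing in 8.4 to 8.4.3 defines duration, gives a censoring rule for it, or mentions competing events or cumulative incidence. Section 8.4 rules out imputation of missing data.

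**The concern.** A viremic subject who dies, starts chronic dialysis for graft loss or is re-transplanted leaves the study without meeting the resolution criterion. A single-group Kaplan-Meier analysis has one event, so this subject can only be censored. The curve then describes how fast viremia would clear if such exits did not occur, and it does so correctly only if the subjects who left would have cleared at the same rate as those who stayed. The background (2.1.1) gives reason to doubt that. It says that "in some studies 30 to 70% of patients with BKVN have progressive deterioration in renal function", ending in loss of the graft, and names persistent viral infection as one of the causes.

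At stake is a basic natural-history figure: of the patients who become viremic, how many clear, how many lose the graft or die first, and how many remain viremic. The study is meant to identify patients for future intervention studies, and these proportions would inform their planning. One minus Kaplan-Meier does not give them. It can approach 100% whatever share of subjects left without clearing.

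**Working it through.** The plan states no expected duration, clearance rate, precision or exit rate for this endpoint, so there is no plan figure to reproduce.

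**Inputs from the documents.** About 40 viremic subjects, at most 60 (4.3); sampling every 2 weeks ± 7 days (4.3); at most 24 months of participation (Protocol Summary).

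**Assumptions, not in the documents.** Constant hazards of clearance (λ) and of exit by death or graft loss (μ); a Kaplan-Meier median of 3 months, with 6 months as a check; a share p of viremic subjects who exit before clearing, of 3%, 5%, 10% or 20%.

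**Formulas.**
- λ = ln 2 / median. For 3 months, λ = 0.6931/3 = 0.2310 per month.
- p = μ/(λ+μ), so λ+μ = λ/(1−p).
- One minus Kaplan-Meier: 1 − exp(−λt).
- Cumulative incidence of clearance: F(t) = (1−p)·[1 − exp(−(λ+μ)t)].
- Time by which half of all viremic subjects have cleared: −ln[1 − 0.5/(1−p)]/(λ+μ).

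**Results at a 3-month median.** One minus Kaplan-Meier at 12 months is 1 − exp(−0.2310 × 12) = 93.8% for every p. Worked case p = 10%: λ+μ = 0.2310/0.90 = 0.2567; F(12) = 0.90 × (1 − exp(−3.081)) = 0.90 × 0.954 = 85.9%.

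| p | of 40 | 1−KM at 12 months | F(12) | gap, points | half cleared by, months (KM 3.00) |
|---|---|---|---|---|---|
| 3% | 1.2 | 93.8% | 91.4% | 2.3 | 3.04 |
| 5% | 2 | 93.8% | 89.9% | 3.9 | 3.07 |
| 10% | 4 | 93.8% | 85.9% | 7.9 | 3.16 |
| 20% | 8 | 93.8% | 77.5% | 16 | 3.40 |

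**At a 6-month median.** One minus Kaplan-Meier at 12 months is 75.0%, against F(12) of 73.8%, 72.9%, 70.7% and 65.9%. Half have cleared by 6.08, 6.14, 6.32 and 6.79 months. The gaps at 12 months are smaller, and the proportional shift in the median is unchanged.

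**Finite-sample check.** In a simulation of 40 subjects with two-weekly sampling and a 3-month median, one minus Kaplan-Meier at 12 months averaged 0.94 at p = 5%, 10% and 20%, against 0.90, 0.85 and 0.76 actually cleared. The medians fall on the sampling grid. They did not differ at 5% or 10%, and were 3.2 against 3.7 months at 20%.

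**Timing.** Until the first competing exit, one minus Kaplan-Meier and the cumulative incidence are the same curve. If every exit comes after half the subjects have cleared, the two medians are identical. A simulation with 10%, 15% and 24% of subjects never clearing and losing the graft at months 6 to 18 confirmed this: the medians were 3.48, 3.80 and 4.68 months by either method.

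**The case against.** The strongest reply is that the summary the plan promises is the median, and the median hardly moves. At p = 10% the shift is 0.16 months, under a week, with visits two weeks apart. With 40 subjects and a 3-month median, the standard error of the median is about 1/(λ√40) = 1/(0.2310 × 6.325) = 0.68 months, larger than any shift in the table. The constant exit hazard also places many losses early, whereas 2.1.1 describes decline over months and 5.3.2 excludes proven or suspected BKVN. This stands, and it places the problem in the clearance curve and the percentages read from it.

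Several stronger readings are tempting, but the documents do not support them.
- A reader might combine the BKVN rates and the 30 to 70% in 2.1.1 into a graft-loss rate for this cohort. Those losses are eventual, come from some studies, and need not precede clearance or fall within 24 months. BKVN is given as 1 to 10%: at 1%, 4.5 cases × 30 to 70% is 1.4 to 3.2 of 40 (3 to 8%), but at 10% the 45 cases exceed the 40 viremic subjects. No usable rate follows.
- A reader might infer that clearance is impossible after graft loss. Resolution is a blood PCR result. Only death plainly precludes it; otherwise observation stops.
- A reader might infer that those who exit are the persistently viremic. That is plausible, but 2.1.1 also names rejection after reduced immunosuppression and fibrosis.
- A reader might count any dialysis as an exit. Section 6.4 ends follow-up only for chronic dialysis due to graft loss.

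Two further replies have some force. The wording in 8.4.2 leaves other methods open and does not itself state that these exits are censored; that follows from the resolution definition combined with Kaplan-Meier. And the direction depends on what duration means. If it were time viremic until any end, Kaplan-Meier would be too long (3.00 against 2.40 months at p = 20%). Both are reasons to write the definition down. Deaths, dialysis and re-transplantation are also reported as separate secondary outcomes (3.2.2), but not as shares of viremic subjects alongside clearance.

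**Conclusion.** The concern holds for the proportion cleared. If any viremic subject dies or leaves through graft loss before clearing, one minus Kaplan-Meier from then on exceeds the proportion who actually clear, whether or not those exits are related to viral persistence. Under constant hazards and an assumed 3-month Kaplan-Meier median, the excess at 12 months is 2 to 16 points for exit shares of 3% to 20%; at an assumed 6-month median it is 1 to 9 points. The exit shares and medians are illustrations, since the documents supply neither.

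The effect on the median is small (up to 0.40 months in the 3-month illustration), and nil if exits follow the median clearance time. A reader should not conclude that the planned median is materially understated. The change is still worth making before the data are seen: the quantity is undefined, the only estimator named for the curve does not give the clearance proportion, and the alternative reduces to one minus Kaplan-Meier when no such exits occur.

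**What to change.** In 8.4.2:

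1. Define duration as time from the qualifying blood sample to resolution as given in 4.3.
2. Replace Kaplan-Meier for this endpoint by the Aalen-Johansen cumulative incidence of clearance. Treat death and graft loss that ends follow-up (chronic dialysis or re-transplantation) as competing events. Keep ordinary withdrawal and study closure as censoring.
3. At fixed times from the qualifying sample, for example 3, 6 and 12 months, report the percentages cleared, lost the graft or died, and still viremic, with counts by reason for leaving. Take the median from the cumulative incidence curve, and say that it is not reached if the curve stays below 50%.
4. State that the Cox model for duration estimates the cause-specific hazard of clearance.

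No new data are needed. The reason for discontinuation goes on the termination page (6.5), and death, dialysis and re-transplantation are recorded at each intensive-phase visit (6.3). The cost is SAP wording and a little more analysis. The only downside is a median that may be slightly longer, or not reached.
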